### **6.2.2. Continuous Secondary Endpoints**

Continuous secondary endpoints include percent CFB in EASI total score, CFB in PASI total score, and percent CFB in affected BSA.

- Estimand strategy: Secondary estimand ([Section 2.2.2](#)). This estimand is intended to provide an estimate of the treatment effect in the absence of prohibited medication use in a population that may or may not be fully compliant with the treatment.
- Analysis set: ITT Analysis Set ([Section 4](#)).
- Analysis methodology: A landmark analysis of these continuous endpoints at Week 12 will be performed by ANCOVA with baseline as a covariate. Missing data, except missing due to COVID-19 pandemic, will be imputed using a control-based imputation method. PROC MI will first be called to impute missing vehicle observations under the assumption data are missing at random (MAR) and impute

missing active treatment observations assuming they are similar to corresponding vehicle arm. The imputation will utilize ANCOVA model including baseline as a covariate fitted using only vehicle arm data. The analysis will combine the results from the multiple imputations using Rubin's rule's as implemented in SAS PROC MIANALYZE. MMRM models may also be used on observed data at all time points as sensitivity analyses. The fixed effects of treatment, visit, and treatment by visit interaction will be included. Baseline value will be included as a covariate. No adjustments for multiplicity will be made.

- Intercurrent events and missing data: A) Prohibited medication: all scores measured at time points after start date of the event for participants who receive prohibited medication post randomization will be excluded from the analysis and treated as missing scores. Missing scores will be imputed. B) Withdrawal and all other events leading to missing data, except COVID-19 pandemic: all missing scores will be imputed. C) COVID-19 pandemic: if a participant misses a visit due to COVID-19, he/she will be excluded from the analysis for that visit; If a participant discontinues treatment or withdraws from the study due to COVID-19, he/she will be excluded from the analyses after the treatment discontinuation visit or study withdrawal visit, respectively. D) Inadequate compliance – participants data will be used as recorded.
- The least-squares (LS) means, the 95% confidence interval for the LS means, the difference between the LS means for each pair of treatment groups, and the corresponding 95% confidence interval will be presented.

### **6.3. Tertiary/Exploratory Endpoints**

#### **6.3.1. Binary Tertiary/Exploratory Endpoints**

CCI

#### **6.3.2. Continuous Tertiary/Exploratory Endpoints**

CCI

CCI

### 6.3.3. PRO Endpoints

CCI

## 6.4. Other Endpoint(s)

### 6.4.1. PK Endpoints

PF-07038124 concentration data will be summarized through appropriate data tabulations, descriptive statistics, and graphical presentation. A population PK model may be developed for the purpose of estimating PK parameters. In addition, a relationship between doses/exposures and efficacy/safety endpoints may be evaluated using population PK/pharmacodynamic (PD) approach. Details of the methodology will be captured in a separate modeling plan and the results will also be reported separately.

## 6.5. Subset Analyses

Proportion of IGA/PGA success at Week 12 may be summarized for the subsets below if we have sufficient number of participants in each stratum:

- Baseline Disease Severity: mild/moderate for AD and mild/moderate/severe for PsO.

## 6.6. Baseline and Other Summaries and Analyses

### 6.6.1. Baseline Summaries

Demographic and baseline characteristics will be summarized by treatment for the safety analysis set. Key demographic and baseline variables include age, gender, race, ethnicity,

height, weight, body mass index, disease duration, baseline affected BSA (%), EASI and IGA score for AD participants, PASI and PGA for PsO participants.

#### **6.6.2. Study Conduct and Participant Disposition**

Participants' evaluation for analysis populations, disposition and discontinuation will be summarized according to CaPS.

#### **6.6.3. Study Treatment Exposure**

The exposure to study drug measured by number of days with dosing will be summarized. The number and percent of participants in exposure duration categories (<1 week to >12 weeks with 1 week increments) will be presented. A summary of dosing compliance, defined as % days with dosing out of the duration between first and last dosing, will be provided by treatment. Number of percent of participants with treatment non-compliance (compliance < 80% or more than 120% of study intervention application) will also be summarized. Ointment application rate, defined as amount of ointment applied per dose(mg) divided by treated BSA (cm\*\*), will also be summarized by treatment and time. The treated BSA at subsequent visits should be equal to or greater than the value at Day 1 (Protocol section 8.9), and different from affected BSA as efficacy endpoint.

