## 4. STUDY DESIGN

### 4.1. Overall Design

This is a phase 2b, randomized, double blind, vehicle controlled, parallel group, multicenter study to assess the efficacy, safety and tolerability, and PK of multiple doses of PF-07038124 ointment versus vehicle in treatment of participants, 12 years and older, and with AD or PsO.

In this study, a total of approximately 240 participants with AD or PsO will be randomly assigned to study intervention (PF-07038124 or vehicle).

Participants will be screened for eligibility to participate in the trial within 4 weeks of randomization, on Day 1. During Screening period, participants will begin documenting their disease symptoms in the e-diary, at least 7 days prior to randomization. After confirming eligibility on Day 1, as outlined in [Section 1.3.1](#) and [Section 1.3.2](#) for AD and PsO respectively, randomization will occur and treatment with the study intervention will begin. Treatment with study intervention (PF-07038124 ointment or vehicle ointment) will be once daily for 12 weeks followed by a safety follow-up period of 4-5 weeks from last application of study drug to last study visit. The total duration of study participation is approximately 21 weeks.

- For AD, approximately 120 participants will be randomly assigned 1:1:1 to receive either 0.01% PF-07038124 ointment, 0.03% PF-07038124 ointment or a vehicle ointment.
  - Randomization will be stratified by baseline disease severity (mild [IGA = 2] vs moderate [IGA = 3]) and by tape stripping sub-study participation. [CCI](#) [REDACTED]
- For PsO, approximately 120 participants will be randomly assigned 1:1:1:1 to receive either 0.01% PF-07038124 ointment, 0.03% PF-07038124 ointment, 0.06% PF-07038124 or a vehicle ointment.
  - Randomization will be stratified by baseline disease severity (mild [PGA = 2], moderate [PGA = 3], severe [PGA = 4]) and by tape stripping sub-study participation. [CCI](#) [REDACTED]

[figure not shown]

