### **6.4. Study Intervention Compliance**

Participants will be instructed to bring to the clinic all used, partially used and empty study intervention tubes in their original containers for weighing, at each visit.

Participant compliance with study intervention will be assessed on visits identified in the [SoA](#). Compliance will be assessed by review of the participant/caregiver completed dosing diary section of the e-diary and thorough review of dosing instructions at every visit. The difference in weight(s) of the returned study intervention tubes will be used to estimate the doses applied at the end of the study. Source documents will be placed in the participant's study file. Deviation(s) from the prescribed dosage regimen should be recorded in the CRF.

From Day 1 through Week 12 visit, non-compliance is defined as application of study intervention less than 80% in a week or more than 120% of study intervention applications. If non-compliance is identified, or even if a few dose applications are missed or over-applied (as informed by the participant to the site staff), then, participants will be re-trained on the importance and the process of proper study intervention application. If non-compliance persists, the investigator, in consultation with the sponsor, may withdraw any participant from the study for reasons of non-compliance with the dosing regimen. Investigators should indicate on the appropriate CRF page noncompliance with study intervention and provide an explanation.

Inventory control of all study intervention must be rigorously maintained throughout the duration of the study until all medication has been accounted for and/or returned to the sponsor. Any discrepancies noted between drug dispensing records and the drug inventory must be reported to Pfizer.

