### 2.1. Modifications to the Analysis Plan Described in the Protocol

NA

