## **6. ANALYSES AND SUMMARIES**

### **6.1. Primary Endpoint(s)**

#### **6.1.1. Main Analysis**

- Estimand strategy: Primary Estimand ([Section 2.2.1](#)). This estimand is intended to provide an estimate of the treatment effect in the absence of prohibited medication use in a population that may or may not be fully compliant with the treatment.
- Analysis set: ITT Analysis Set ([Section 4](#)).

- Analysis methodology: A landmark analysis of the IGA/PGA success endpoints at Week 12 will be performed using the ITT analysis set. The proportions responding and the corresponding risk difference comparing active treatment arm to vehicle group will be analyzed using the unconditional exact method; the risk differences and the corresponding 2 sided unconditional exact 95% confidence intervals will be computed using Chan and Zhang (1999) method. The overall family wise Type I error rate will be controlled at the 1 sided 0.025 level using the Hochberg step up procedure.
- Intercurrent events and missing data: A) Prohibited medication – response will be considered as failure for time points after start date of the event for participants who receive prohibited medication post randomization. B) Withdrawal and all other events, except COVID-19 pandemic, leading to missing data will be treated similarly assuming that participants no longer receive benefit from the study intervention and hence will be considered as failure. C) COVID-19 pandemic: if a participant misses a visit due to COVID-19, he/she will be excluded from the analysis for that visit; If a participant discontinues treatment or withdraws from the study due to COVID-19, he/she will be excluded from the analyses after the treatment discontinuation visit or study withdrawal visit, respectively. D) Inadequate compliance – participants data will be used as recorded.
- Proportions, risk differences and 95% confidence intervals will be presented.

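### SAP 6.6.3 counts treatment non-compliance at the protocol's 80% cut-off but over the whole dosing period, whereas protocol 6.4 sets that limit per week, so the reported count will not match the protocol definition.

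*SAP*

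**What the plan says.** Protocol 6.4 (Study Intervention Compliance) gives the protocol's only definition. It runs from Day 1 to the Week 12 visit: "non-compliance is defined as application of study intervention less than 80% in a week or more than 120% of study intervention applications". Sites act on it. They retrain the participant and record the non-compliance with an explanation on the CRF. Beyond that, "If non-compliance persists, the investigator, in consultation with the sponsor, may withdraw any participant from the study".

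SAP 6.6.3 (Study Treatment Exposure) first defines a single percentage per participant: "A summary of dosing compliance, defined as % days with dosing out of the duration between first and last dosing". The next sentence counts participants with "treatment non-compliance (compliance < 80% or more than 120% of study intervention application". The weekly unit does not appear.

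SAP 2.1, headed "Modifications to the Analysis Plan Described in the Protocol", has the entry NA. For the estimands, non-compliance changes nothing in the data: "Inadequate compliance – participants data will be used as recorded" (SAP 6.1.1, with the same rule in 6.2.2).

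**The concern.** One label and one pair of cut-offs are used over two time bases: 7 days in the protocol and about 84 days in the SAP. A programmer following SAP 6.6.3 will produce a table headed non-compliance that does not count the participants protocol 6.4 calls non-compliant. It need not agree with the non-compliance entries that sites make on the CRF.

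The table has a use. Both estimands apply regardless of compliance, so someone asking whether a weak dose response reflects the drug or under-use will look here. Persistent non-compliance can also end in withdrawal, and data missing after withdrawal count as failure for the binary endpoints. A reader tracing such withdrawals would expect the table to follow the rule behind them.

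**Working it through.** The documents state no expected non-compliance rate, so there is no figure of theirs to reproduce.

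**Inputs**
- Weekly limit of 80%: protocol 6.4.
- Whole-period ratio with the same 80%: SAP 6.6.3.
- Schedule: "Treatment with study intervention (PF-07038124 ointment or vehicle ointment) will be once daily for 12 weeks" (protocol 4.1), i.e. 7 applications a week and 12 × 7 = 84 in all.
- Daily adherence p: an assumption, shown as a range.

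**The rules as counts**
- Weekly: 80% of 7 is 5.6, so 5 or fewer applied (2 or more missed) fails; 5/7 = 71.4%, 6/7 = 85.7%.
- Whole period: 80% of 84 is 67.2, so 67 or fewer dosed days (17 or more missed) fails. Counting 85 days, 68/85 is exactly 80%, so 18 misses are needed.

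**Cases that need no adherence assumption**
- Two misses in one week: 71.4% for that week, 82/84 = 97.6% overall.
- Two misses in each of 8 weeks: the weekly limit fails 8 times, yet (84 − 16)/84 = 68/84 = 81.0% overall.
- If no week falls below 6/7, the overall figure is at least 72/84 = 85.7%. So over 12 full weeks anyone under 80% overall has also failed at least one week, and the SAP count cannot exceed the weekly-rule count.

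This ordering is limited to full weeks. Someone who misses one day in week 1 and Day 8, then stops after a Day 9 dose, has 7/9 = 77.8% overall but 6/7 in the only complete week. The result then depends on how a partial week is treated.

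**Size with one common p and independent days**

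One week fails with probability w = P(Bin(7, p) ≤ 5); at least one of 12 fails with probability 1 − (1 − w)^12; the whole period fails with probability P(Bin(84, p) ≤ 67).

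| p | w | at least one week under 80% | under 80% overall |
|---|---|---|---|
| 0.98 | 0.0079 | 9.0% | <0.01% |
| 0.97 | 0.0171 | 18.7% | <0.01% |
| 0.95 | 0.0444 | 42.0% | <0.01% |
| 0.92 | 0.1026 | 72.7% | 0.03% |
| 0.90 | 0.1497 | 85.7% | 0.4% |
| 0.85 | 0.2834 | 98.2% | 11.9% |

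**Size when adherence varies between participants**

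Let p follow a beta distribution with mean m and parameters summing to s, so its SD is √(m(1 − m)/(s + 1)).
- m = 0.95, s = 20 (SD 0.048): 36% with a failing week, 2% under 80% overall. s = 10 (SD 0.066): 32% and 5%.
- m = 0.90, s = 20 (SD 0.065): 68% and 11%. s = 10 (SD 0.090): 59% and 15%.

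Taking the common-p case together with these two spreads gives 32-42% against 0-5% at mean 0.95, and 59-86% against 0.4-15% at mean 0.90. A still wider spread (m = 0.90, s = 5) narrows the gap to about 49% against 17%.

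For an AD arm of 40 at mean 0.95 this is about 13 to 17 participants (0.32 × 40 = 12.8; 0.42 × 40 = 16.8) against 0 to 2 (0.05 × 40).

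**The case against.** **The SAP sentence may be shorthand for protocol 6.4.** A percentage of days with dosing cannot exceed 100%, so the 120% limb makes no sense under the SAP's own ratio and looks copied from the protocol. That is plausible as to intent. But the SAP defines compliance in the preceding sentence and uses the same word inside the count, so the whole-period rule is what would be programmed.

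**The purposes differ.** Protocol 6.4 is mainly a trigger for site action, and protocol Section 9 plans no compliance analysis, so NA in SAP 2.1 need not hide a change to a planned analysis. This stands as far as it goes: the documents do not show a concealed departure. The SAP still borrows the protocol's label and cut-offs without saying that the unit has changed.

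**Whole-period adherence is the better exposure measure.** Missing 2 of 84 doses could hardly flatten a dose response, and with 95% of doses applied the weekly rule can flag up to 42% of participants. This stands, and it is why the overall figure should be kept. It does not justify giving that figure the protocol's name for something else.

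**Other data exist.** SAP 6.6.3 also summarises days dosed, exposure duration, the compliance percentage itself and ointment use per dose. These limit the harm, but none of them counts participants by the weekly rule.

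**Any single week is an inference.** The protocol says in a week, without the word any. That is the natural reading, and all the weekly percentages above rest on it.

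A reader might infer that the SAP table will show almost nobody as non-compliant. The documents do not support that. It follows only if every participant shares one high adherence rate with independent misses. With adherence varying between participants, 2-15% still fall under 80% overall in the cases above. The model also ignores retraining and the doses applied in clinic on visit days.

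**Conclusion.** The point holds as a conflict between two stated definitions in one descriptive table. Over 12 full weeks the SAP count equals or understates the count under protocol 6.4; that needs only the once-daily schedule and the reading of in a week as any week. The size of the understatement rests on assumed adherence and its spread between participants, and the ranges above illustrate it; they do not predict it.

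A reader might also suspect that the efficacy results are affected. They are not: data are used as recorded whatever the compliance, so the estimands, type I error and power do not change. This is a minor correction, but the line as written should not carry the protocol's label.

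**What to change.** Reconcile protocol 6.4 and SAP 6.6.3 in the SAP:
- Add, by arm, the number and percent of participants with at least one study week under 80%, and the number of such weeks. Derive them from the daily dosing entries in the e-diary.
- State how a partial last week and the interruptions the protocol permits (7.1.4, 7.1.6) enter the denominator of applications due.
- Keep the whole-period percentage as a separate line labelled overall compliance.

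The cost is one further derivation from data already collected. The drawback is a less favourable reported percentage, because a single week with 5 of 7 applications is enough to be counted. Showing the number of such weeks and the overall line beside it lets the reader weigh that.

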### Day 1 Visit

At the Day 1 visit, before the Day 1 initial study intervention application is performed, the designated areas for treatment will be identified and documented in the participant's source document study records (body map). The participant and/or caregiver will be provided with a paper version of the body map.

Participants and/or caregivers will be encouraged to observe and participate in the initial study intervention application on Day 1.

### Post Day 1

Following Day 1 visit through the final dose at Week 12 visit, the study intervention should be applied once daily (around same time of the day), to all treatable AD or PsO involved areas identified at the Day 1 visit as well as to new areas identified as "treatable" during the course of 12 weeks. All participants will be supplied with instructions on application.

- Note: Any new AD or PsO areas identified by the participant or caregiver(s) should also be treated with the study intervention *after assessment by the investigator or his/her designee*. An unscheduled visit for assessment of the new lesion may be required at the discretion of the Investigator. If the new lesion is identified as treatable, then body map will be updated, and study intervention need will be re-assessed.

The study intervention will be applied at home/residence except on the days of in-clinic visits. **On the days of scheduled in-clinic visit, participants will be instructed to refrain from applying the study intervention at home/residence.** The last dose of study intervention will be applied during the Week 12 in-clinic visit (EOT visit) as specified in the **SoA**.

- Note: If due to public emergency, local regulations don't allow participant to visit the clinic on scheduled visit days, the participant will refrain from applying the study intervention until selected assessments can be completed using televisit or home health visit.

The participant and/or caregiver will be instructed to complete the dosing diary section of the e-diary, starting with the first dose applied in the clinic on Day 1 through Week 12 (each time study intervention is applied). If a participant misses applying a dose, the participant should apply this dose provided this dose should have been applied within the last 6 hours. For longer intervals, the dose should be skipped. The missed dose should be recorded in the dosing diary. The next dose should be applied according to the regular dosing regimen.

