#### **6.7. Treatment of Overdose**

For this study, any dose of study intervention greater than 1 dose within a 12-hour time period will be considered an overdose.

Investigators should be aware that administration to significantly greater area may also be treated as an overdose at investigator discretion.

The sponsor does not recommend specific treatment for an overdose.

In the event of an overdose, the investigator should:

1. Contact the medical monitor within 24 hours.
2. Closely monitor the participant for any AEs/SAEs and laboratory abnormalities for at least 28 calendar days after the overdose of study intervention.
3. Document the quantity of the excess dose as well as the duration of the overdose in the CRF.
4. Overdose is reportable to Pfizer Safety only when associated with an SAE.

CCI

Decisions regarding dose interruptions or modifications will be made by the investigator in consultation with the medical monitor based on the clinical evaluation of the participant.

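### SAP 6.6.3 measures compliance in dosed days, so its >120% category is empty by construction, and it omits the per-week 80% limit of protocol 6.4

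*SAP*

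**What the plan says.** SAP 6.6.3 (Study Treatment Exposure) plans a by-treatment summary of dosing compliance, "defined as % days with dosing out of the duration between first and last dosing". The next sentence plans a count of non-compliant participants, with the rule "compliance < 80% or more than 120% of study intervention application". No other compliance measure is defined in that section.

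Protocol 6.4 gives the rule that these limits come from. From Day 1 through the Week 12 visit, "non-compliance is defined as application of study intervention less than 80% in a week or more than 120% of study intervention applications". Two features matter: the unit is the application, and the lower limit is tested by week.

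The planned regimen is in protocol 6.1.1: "Following Day 1 visit through the final dose at Week 12 visit, the study intervention should be applied once daily". The Schedule of Activities puts the Week 12 visit at Day 85, plus or minus 2 days. Protocol 6.1.1 also asks for the dosing diary to be completed at every application.

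SAP 2.1, which is the place to list departures from the protocol's analysis plan, is marked not applicable.

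**The concern.** The two sentences in SAP 6.6.3 do not fit together. A count of dosed days divided by the days in the same interval is bounded at 100%, and a limit of 120% is then applied to it. If the limit is programmed on the ratio just defined, nobody can exceed it.

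Over-use is an event that the protocol foresees. Protocol 6.4 provides for retraining when doses are over-applied, and protocol 6.7 states that "any dose of study intervention greater than 1 dose within a 12-hour time period will be considered an overdose". A table with nobody above 120% would read as evidence that over-application did not happen, when the measure could not have shown it.

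The lower limit has also changed meaning. A weekly test in the protocol has become one figure over the participant's whole dosing span, so a short lapse is averaged away. The estimands apply regardless of compliance and the trial compares strengths. A reader of a weak or flat dose response will look to this table to judge how the ointment was used.

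**Working it through.** **Inputs**
- SAP 6.6.3: compliance = days with dosing / days from first to last dose; limits <80% and >120%.
- Protocol 6.4: limits on applications, with the 80% limit per week.
- Protocol 6.1.1 and Schedule of Activities: one application a day to Day 85 (range 83 to 87), so 85 planned applications.

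The plan states thresholds here, not a calculated figure, so there is nothing to reproduce first.

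**1. Upper bound.** Let F and L be the first and last dosing days and D the number of distinct days with dosing. All D days lie between F and L, so D ≤ L − F + 1 and

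compliance = D / (L − F + 1) ≤ 100%.

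A check over 200,000 simulated dosing calendars gave a maximum of exactly 1.000.

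**2. Day-count convention.** The SAP does not say whether both end days count. If the duration were L − F, daily dosing over n days would give n/(n − 1):

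| Dosing span (days) | n/(n − 1) |
|---|---|
| 85 | 85/84 = 101.2% |
| 6 | 6/5 = 120.0% (not above 120%) |
| 5 | 5/4 = 125.0% |
| 2 | 2/1 = 200.0% |
| 1 | undefined |

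Only spans of 2 to 5 days could exceed 120%. That would be a counting artefact, not over-application.

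**3. Over-use.** On applications, 120% of 85 is 1.2 × 85 = 102, so 103 or more applications cross the limit. Two applications on each of 85 days:
- applications: 170/85 = 200%;
- SAP measure: 85/85 = 100%, because a second application on the same day adds no dosed day.

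**4. Weekly under-use.** The participant doses on Day 1 and Day 85, and all missed days fall in one week between them:

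| Missed in that week | That week (protocol 6.4) | Whole span (SAP 6.6.3) |
|---|---|---|
| 2 days | 5/7 = 71.4%, non-compliant | 83/85 = 97.6%, compliant |
| 7 days | 0/7 = 0%, non-compliant | 78/85 = 91.8%, compliant |

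Over 85 days, 17 missed days still give 68/85 = 80.0%, which is not below the SAP limit.

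**5. Early stopping.** Daily dosing that stops after Day 28 scores 28/28 = 100% in the SAP, against 28/85 = 32.9% of planned doses (32.2% to 33.7% for 87 to 83 planned).

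**The case against.** The best defence is that the SAP's 120% phrase echoes the application wording of protocol 6.4, so an application count may have been intended. That is plausible, but the SAP defines no such count. On that reading the category is unspecified instead of empty, and the text still needs correcting.

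A second defence is that the weekly 80% rule is a conduct trigger, leading to retraining and possibly withdrawal, and that the protocol does not require it to be tabulated. That has some force. However, the SAP reuses the same limits under the same label, so its count of non-compliant participants will not match the protocol's definition, and no departure is declared.

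Three stronger conclusions might be inferred, and the documents do not support them.
- *The table will look near-perfect whatever happens.* It will not. Missed days inside the span lower the ratio: alternate-day use scores about 50% and is flagged.
- *Early stopping and true exposure are hidden.* They are hidden only from this ratio. SAP 6.6.3 also summarises the number of dosing days and "exposure duration categories (<1 week to >12 weeks with 1 week increments", and SAP 6.6.2 covers disposition and discontinuation. Ending the denominator at the last dose is a defensible measure of adherence while on treatment. A denominator running to Week 12 would mark down participants whom the protocol itself requires to stop.
- *Over-use goes unrecorded in the trial.* Dosing deviations (protocol 6.4) and overdoses (6.7) go on the CRF, and the SAP summarises the ointment application rate. That rate is per dose, however, so it does not count applications.

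**Conclusion.** The SAP rule is wrong as written, and the consequence is limited to one descriptive summary. With an inclusive day count, the >120% category contains nobody by construction, so the table would show no over-application even if it occurred. The measure also misses weeks that protocol 6.4 calls non-compliant: 71% for the week against 98% over 85 days in the simplest case. SAP 2.1 does not disclose the change.

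This rests on the 120% limit being applied to the ratio that the SAP defines, on both end days being counted, and on about 85 planned once-daily applications.

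It would go too far to infer that the efficacy conclusions are at risk. Under both estimands, data from participants with inadequate compliance are used as recorded, and no analysis set or test visible in the SAP depends on this ratio. The primary analysis, power and alpha are unaffected.

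**What to change.** In SAP 6.6.3:
1. Define compliance as e-diary applications divided by planned once-daily applications over the on-treatment period, with first and last day both counted.
2. Apply the >120% limit to that application count, and report it separately from under-use.
3. Flag each participant with any week below 80%, as in protocol 6.4. Say how weeks are cut (85 days is 12 weeks plus one day) and how interruptions allowed by the protocol enter the planned count.
4. If the days-based ratio is kept as an extra line, remove the 120% limit from it and state the day-count convention.
5. Record in SAP 2.1 any difference from protocol 6.4 that remains.

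A further column against all planned doses to Week 12 is optional, since exposure duration and disposition already show early stopping.

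The cost is SAP wording and minor programming. No new data are needed, provided the diary accepts more than one entry a day. Protocol 6.1.1 implies this, but it should be confirmed.
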